ongoing activity that students can participate in until they leave or graduate from school. Girls participating in the SOC Arm (SKILLZ-Girl) are able to join any of the other clubs currently offered at their school (SOC Clubs).

Clubs have been operating in schools in Zambia since 2017 with the MOGE's consent as part of the Memorandum of Understanding (MOU) signed in 2010 (*see Appendix B*). The CLUB component is currently evolving to include a more formalized education component, and will be piloted in Zambia at the same time as this evaluation.

4. All girls who test positive for HIV (whether prior to the SKILLZ-Girl event, during the event or as part of their participation in SKILLZ-Club) are referred to **SKILLZ-Plus**, a clinic-based initiative which provides HIV-infected girls access to ongoing support through a 12-week curriculum. During follow-up in the SOC Club arm, study staff will refer any newly identified HIV-positive girls to SKILLZ-Plus. In addition, study staff will refer newly diagnosed girls aged 16 years from neighboring clinics to the SKILLZ-Plus intervention.

For girls who test positive for HIV, either through a:

1. school referral either at the event, during club participation, are identified during follow-up or with a previously known diagnosis or
2. clinical referral (newly diagnosed only)

In addition, all girls found to be HIV-positive at any point throughout the SKILLZ-Program will be provided with intensive counselling support. Coaches will facilitate a family visit to facilitate disclosure and work with CIDRZ networks to provide additional psycho-social support as needed on a case-by-case basis by the participant.

SKILLZ-Plus provides several additional features:

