Within SKILLZ-Girl and SKILLZ-Club, our study will examine the additional benefits of offering access to two new health service offerings that are expressly designed to overcome barriers to uptake especially difficult for adolescents to overcome—HIV self-testing (HIVST) kits and access to an expanded method mix for contraceptive methods. Referral for contraceptive and SRH services will be made to the PEPFAR-funded DREAMS Houses or youth corners at local government facilities which are located within close distance to all schools where the SKILLZ package will be implemented.

Our mixed-methods evaluation will assess the effects of the enhanced SKILLZ offering (SKILLZ-Girl Enhanced & SKILLZ Club programs) compared to the SOC SKILLZ offering of SKILLZ-Girl only. Although the SKILLZ Program (Enhanced or SOC pending school allocation) will be offered to all girls enrolled in Grade 10 at selected study secondary schools, only girls aged 16 and over at the commencement of SKILLZ-Girl will be enrolled into the research study.

We will examine outcomes for school girls aged 16 and over enrolled in Grade 10 at the start of the intervention in up to 16 schools where the SOC SKILLZ Package is offered, compared to outcomes in up to 16 schools where the enhanced SKILLZ-Package is offered, including HIVST, the availability of expanded contraceptive services and the SKILLZ-Club following completion of SKILLZ-Girl. Therefore, all schools will be preassigned prior to the intervention into the following 2 categories (see **Figure 3** in *Section 8 - Methodology* below).

1. **SOC:** SKILLZ-Girl → Club SOC
2. **ENHANCED:** SKILLZ-Girl enhanced → SKILLZ-Club

Our central hypothesis is that the additional offering of HIVST and contraceptive services in an enhanced SKILLZ-Girl combined with the SKILLZ-Club offering will increase HIV testing and contraceptive uptake and continuation.

In addition to SKILLZ-Girl and SKILLZ-Club, girls testing HIV-positive at any time during the study intervention period will be additionally offered to participate in the SKILLZ-Plus facility-based curriculum for HIV-infected adolescents. The effect of the SKILLZ-Plus curriculum will be tested using a SmartCare-derived matched (i.e., on clinic, age, ART start date and gender) population.

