Difference-in-difference model. The primary outcome is the probability of testing for HIV at any time during the period when SKILLZ is delivered through to 24 months after the final soccer event. The primary analysis for Aim 1 will follow a difference-in-difference (DID) effect between study arms. The outcome of interest will be regressed on an indicator of study arm assignment interacted with a dichotomous variable POST which indicates the outcome after the intervention is implemented; this differentiates baseline and end-line for each study arm, controls for any time dependent variables that might confound the effect, as well as any time-invariant observed or unobserved confounders that might differ between study arm schools. Because of this, the DID is robust to time-invariant unobservable confounders (e.g., school quality) and time trends (e.g., secular increase in testing). Our estimator relies on the assumption of common time trends across intervention and control in absence of the intervention, and of static population. Additionally, we control for baseline individual and school-level moderators that may be unbalanced at baseline after randomization. School-level controls include size, promotion rates, sex composition and repetition and dropout rates (available in the district education office) and individual girls' controls include age, grade, maternal education, HIV knowledge. Clustering by school will be accounted for by a generalized estimating equation approach. We will estimate intention-to-treat (ITT) by including all girls in the evaluation cohort assigned to each arm rather than all girls who actually participated in SKILLZ.

Individual-level matched cohort analysis for HIV-infected: The analysis will follow an individual ITT estimator among individuals found to be HIV-infected, who will then be matched (based on clinic, age, ART state date, and gender) to HIV-infected individuals in the SmartCare database. The outcomes are the proportion of enrolled HIV+ girls who linked to care, who are virally suppressed and retained in care at 6, 12, and 24 months after diagnosis of HIV+ (using national electronic HIV medical record data). We will conduct an ITT analysis for the logistic probability of being suppressed at 6, 12, and 24 months after HIV+ diagnosis, where girl is the unit of analysis. All data will be analyzed using STATA.

Process evaluation: This will involve quantitative and qualitative analyses:

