Economic evaluation: We will assess cost-effectiveness in three steps. First, we will assess the net cost of the intervention and its consequences, using micro-costing and modeling techniques. Costs for the intervention itself will include mainly personnel to manage the intervention and the financial incentives. Costing of the intervention and control models will be captured in costing sheets that will be prepared before the start of the intervention aimed at capturing costs as they are spent; we will limit the costing from the provider perspective and will only limit costing to programmatic and not research costs. We will also cost the change in health care utilization precipitated by the intervention: both increased preventive care and decreases in curative care. This will be assessed combining utilization with standard values for unit cost (per MOH official records). Together, these generate net costs. Second, we will quantify the health benefits of the intervention, including health events (e.g., number and type of opportunistic infections, STIs) and Quality-Adjusted Life Years (QALYs) which translate morbidity in the short and long term (projected based on published longitudinal clinical studies) into a standard metric of health status. Health state utility data (for QALYs) will derive from studies in the literature. The analysis of expected costs and QALYs in the intermediate and long-term will be structured using a spreadsheet-based decision analysis created for this purpose in consultation with clinical experts. Third, we will calculate the economic outcome measures including the Incremental Cost-Effectiveness Ratio (ICER) and Return-on-Investment (ROI). The ICER is the ratio of net cost to health gain, comparing the SKILLZ-Plus to control (e.g., ICER for

HIV testing = $(C_{\text{intervention}} - C_{\text{control}}) / (\text{Testing rate}_{\text{intervention}} - \text{Testing rate}_{\text{control}})$, and is indicated if the intervention has a net cost (i.e., does not save money) while improving health outcomes (QALYs gained). All analyses will be repeated for 1, 2, 5, 10, & 20 years, and subjected to extensive sensitivity analyses to test the impact of uncertainty on results.

9. Ethical considerations

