Study participants will receive no direct benefits for participating in the study. They will not be given any money for participating in the study. Those pupils invited to attend a focus group discussion will be given refreshments during the discussion. In cases where focus group discussions are held on weekends, students will be given a transport reimbursement in addition to refreshments. A K100 will be provided for transport reimbursements and lunch allowances where necessary.

10. Timelines

Timeline	2018		2019				2020				2021				2022			
	Q3	Q4	Q1	Q2	Q3	Q4	Q1	Q2	Q3	Q4	Q1	Q2	Q3	Q4	Q1	Q2	Q3	Q4
Protocol development and planning																		
IRB/ REC submission																		
IRB/REC Approval																		
Study preparation																		
Recruitment																		
Participant follow up																		
Data cleaning and analysis																		
Study close out activities																		
Dissemination of results																		

11. Budget

	Year 1	Year 2	Year 3	Year 4	Year 5
Salaries and Wages	ZMK 235,082	ZMK 235,082	ZMK 235,082	ZMK 262,469	ZMK 262,469
Fringe Benefits	ZMK 73,838	ZMK 73,838	ZMK 73,838	ZMK 83,536	ZMK 83,536
Personnel Costs (Subtotal)	ZMK 308,920	ZMK 308,920	ZMK 308,920	ZMK 346,006	ZMK 346,006
Travel				ZMK 37,624	
Other	ZMK 82,163	ZMK 82,163	ZMK 82,163	ZMK 82,163	ZMK 82,163
Subaward/Consortium/Contractual Costs	ZMK 5,380,354	ZMK 4,901,077	ZMK 4,880,127	ZMK 4,835,098	ZMK 4,629,423
TOTAL Direct Costs	ZMK 5,767,853	ZMK 5,292,159	ZMK 5,271,210	ZMK 5,300,891	ZMK 5,057,591
Facilities and Administrative Costs	ZMK 423,522	ZMK 101,679	ZMK 101,679	ZMK 121,100	ZMK 111,318
TOTAL COST	ZMK 6,191,375	ZMK 5,393,839	ZMK 5,372,889	ZMK 5,421,991	ZMK 5,168,909

12. Appendices

a. Letter of Permission from MOGE for GRS to continue working in schools in 2019

All Correspondence should be addressed
to the District Education Board Secretary

[contact]
E-mail: [contact]

REPUBLIC OF ZAMBIA
MINISTRY OF GENERAL EDUCATION

DISTRICT EDUCATION BOARD SECRETARY
[name]
LUSAKA

In reply please quote

12th February, 2019

The Country Director
Grassroot Soccer
Lusaka District.

**REF: PERMISSION FOR GRASSROOT SOCCER TO CONTINUE WORKING IN SCHOOL
FOR THE YEAR 2019.**

The subject above refers.

Our office is pleased to once again permit your organization to continue working with both private and government schools in Lusaka District for the year 2019.

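### The cost-effectiveness ratio is defined for SKILLZ-Plus but illustrated with HIV testing, a gain that contrast cannot measure; each ICER needs its own contrast, control and effect

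*Combined protocol and SAP*

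**What the plan says.** The economic paragraph of Section 8f defines the ratio this way: "The ICER is the ratio of net cost to health gain, comparing the SKILLZ-Plus to control". It then gives, as an example, an ICER for HIV testing: the cost difference between intervention and control divided by the difference in their testing rates. No other ICER contrast is named there, and that paragraph does not say who the control group is.

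Other sections describe SKILLZ-Plus as follows.

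- **Who enters.** Section 4 calls it "a clinic-based initiative which provides HIV-infected girls access to ongoing support through a 12-week curriculum". It is reached by referral after a positive test or with a known diagnosis.
- **Which arm.** It is available in both. Section 4 says: "During follow-up in the SOC Club arm, study staff will refer any newly identified HIV-positive girls to SKILLZ-Plus". Newly diagnosed girls from neighbouring clinics are also referred.
- **Compared with whom.** Section 4: "The effect of the SKILLZ-Plus curriculum will be tested using a SmartCare-derived matched (i.e., on clinic, age, ART start date and gender) population". Section 8f confirms that girls found to be HIV-positive are matched "to HIV-infected individuals in the SmartCare database".
- **On what outcomes.** The matched-cohort paragraph of Section 8f lists linkage, viral suppression and retention. HIV testing is not among them.

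HIV testing is the primary outcome of the school comparison, enhanced against SOC (Sections 8c and 8f). Section 2b places the cost-effectiveness comparison between the standard and the enhanced approach. Aim 3 in Section 7 covers the Girl, Club and Plus curricula.

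**The concern.** The named intervention and the example outcome belong to two different comparisons. Testing can differ between school arms because the enhanced arm adds self-test kits, extra curriculum content and SKILLZ-Club. It cannot usefully differ between SKILLZ-Plus participants and their SmartCare matches, because both groups already carry an HIV diagnosis.

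Cost-effectiveness is one of three aims, and the ministries are meant to use the results when deciding on integration into public schools. Their question is whether the enhanced package is worth its added cost over the standard one. An analyst who follows Section 8f literally would get an undefined or uninformative ratio. An analyst who sees the problem would have to choose a contrast after the fact, perhaps with the costs and effects already in view. There is also a risk of a hybrid, with SKILLZ-Plus costs in the numerator and the school-arm testing effect in the denominator.

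**Working it through.** The documents give no cost, QALY or ICER figure, so there is no planned value to reproduce. What can be checked is the denominator of the example ratio under each reading the text allows.

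**Formula.** ICER = (C_I - C_C) / (T_I - T_C), where C is cost per girl, T is the proportion tested, I is intervention and C is control.

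**Inputs.**
- Expected testing uptake in the school arms: 60% control, 80% intervention (Section 8c).
- SKILLZ-Plus participants: all HIV-positive (Section 4), so T = 1.00 if T means ever tested.
- Matched SmartCare group: all HIV-infected and in the care record (Section 8f), so T = 1.00 on the same definition.

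**Reading (a): SKILLZ-Plus versus its documented control, the SmartCare matches.** With T as ever tested, 1.00 - 1.00 = 0 and the ratio is undefined. If T instead follows the primary outcome window in Section 8f (from SKILLZ delivery to 24 months after the final soccer event), girls with a previously known diagnosis may have had no test in that window. The difference then need not be zero, but it reflects the route by which girls became eligible and not any effect of SKILLZ-Plus.

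**Reading (b): SKILLZ-Plus versus the SOC school cohort.** 1.00 - 0.60 = 0.40. The ratio can be computed, at 1 / 0.40 = 2.5 times the cost difference per girl. The 1.00 is produced by the entry condition, so the result is not a programme effect.

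**Reading (c): enhanced versus SOC schools.** 0.80 - 0.60 = 0.20. The ratio is meaningful, at 1 / 0.20 = 5 times the incremental cost per girl for each additional girl tested. This reading requires setting aside the contrast that Section 8f names.

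**Do SKILLZ-Plus costs fit the testing effect?** Section 8a expects about 98% of girls testing to be HIV-negative. Take the target of 3,200 girls (Section 8d), assume an even split between arms, and apply the planning uptake: 1,600 x 0.60 x 0.02 = 19.2 positives in SOC schools and 1,600 x 0.80 x 0.02 = 25.6 in enhanced schools. That is about 45 girls, or 44.8 / 3,200 = 1.4% of the cohort, spread over both arms. Previously known diagnoses and clinic referrals would add to this. SKILLZ-Plus costs therefore arise in both arms and partly outside the schools, and they are not the incremental cost that buys the 0.20.

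**The case against.** The strongest reply is that this is a labelling slip. The formula uses generic subscripts for intervention and control, it is introduced only as an example, and Section 8f plans costing of both intervention and control models. Section 2b and Aim 3 show that enhanced versus standard was always meant to be evaluated. A SKILLZ-Plus ratio on QALYs, suppression or retention would also be coherent under the general definition of net cost over health gain.

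Most of that stands, and it limits the point. Three stronger readings are tempting, and the documents do not support them.

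- **That the printed formula has a zero denominator.** Zero follows only if control means the SmartCare matches and testing means ever tested. The formula says neither, and with the school arms it gives 0.20.
- **That the comparator is wrong.** The economic paragraph leaves control undefined. The mismatch lies in the intervention it names.
- **That the cost list contradicts the ethics section.** Section 8f lists "mainly personnel to manage the intervention and the financial incentives" as the main intervention costs, and Section 9 says of participants: "They will not be given any money for participating in the study". Section 8f names no recipient for the incentives and restricts costing to programme activity, while Section 9 concerns payment for taking part in the research. Both statements can be true, so no contradiction is shown.

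The reply does not rescue the sentence itself. It names one contrast and illustrates it with an outcome on which that contrast has nothing to show. Reading it sensibly means replacing the contrast.

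**Conclusion.** The point holds as an error of specification in the economic analysis. SKILLZ-Plus versus control cannot measure a gain in HIV testing, and the stated contrast does not match Section 2b or Aim 3. The enhanced-versus-SOC comparison is promised elsewhere in the protocol, so it is not absent from the study; the analysis plan does not specify its ratio.

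The testing difference under the named contrast is 0 or uninformative, against a planning difference of 0.20 for the school arms. This rests on the 60% and 80% uptake assumptions and on the descriptions of SKILLZ-Plus and its matched group in Sections 4 and 8f. No effect on an ICER value can be stated, because no costs are given. The consequence is confined to Aim 3; the primary outcome, the sample size and the effectiveness analysis are untouched.

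**What to change.** In the economic paragraph of Section 8f, replace the single contrast with a statement of contrast, control group and effect measure for each ICER:

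1. **HIV testing.** Enhanced SKILLZ-Girl plus SKILLZ-Club versus SOC schools, with arm-specific programme costs and the intention-to-treat effect expressed as an absolute difference in the proportion tested (planning value 0.20). State how SKILLZ-Plus costs are handled, since they arise in both arms.
2. **SKILLZ-Plus.** SKILLZ-Plus versus the matched SmartCare cohort, with its planned outcomes (viral suppression, retention) or QALYs as the effect.

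The allocation delivers the enhanced curriculum and SKILLZ-Club together, so the first ratio covers them jointly. Saying so would align the paragraph with the scope of Aim 3.

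The cost is small. Costing sheets for intervention and control models are already planned, utilisation is to be valued at standard unit costs, and both effect estimates come from analyses already in Section 8f. The wording should be settled before costs and outcomes are combined.

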1.0 Definitions

In this MoU unless clearly inconsistent with or otherwise indicated by the context the following terms shall have the following meanings:

"Beneficiaries" means Zambian youth between the ages of 12 and 18 who benefit from GRS programmes.

"HIV Prevention" means the critical relationships between the epidemiology of HIV infection, the risk behaviours that cause exposure to HIV transmission, and the collective social and institutional factors, such as sexual norms, gender inequality, and HIV related stigma, which will otherwise continue to fuel the HIV epidemic.

FW
N

“Implementing Partners (IP)” means schools, organisations, clubs, academies and other entities working with GRS to incorporate GRS’s specialized curriculum and programme into their programming.

“MoU” means this Memorandum of Understanding.

“NASF 2006 2010” means the current National AIDS Strategic Framework

“Peer Educator” means teachers, mentors, coaches and others trained in the GRS Curriculum

“Programmed Activities” include eight (8) week intervention programmes, VCT tournaments, and ToCs.

“ToC” means Training of Coaches in the GRS Curriculum.

To this end, the MoE and GRS agree as follows:

ARTICLE 2

2.0 Scope of the Agreement

- 2.1 The terms of co-operation for each specific activity under this MoU shall be mutually discussed and agreed upon in writing by both parties.
- 2.2 The Parties agree to promote and co-operate with the view to use the power of soccer in the fight against AIDS, by providing Zambian youth with the knowledge, skills, and support to remain HIV free.
- 2.3 GRS offers HIV and AIDS prevention programmes that uses an evidence-based approach derived from current best practices in HIV prevention in youth, youth communication and sport-for-development to inform a comprehensive communication and outreach strategy.
- 2.4 GRS aims to make a significant contribution to the fight against HIV and AIDS by engaging youth in the fight against HIV and AIDS prevention.
- 2.5 MoE recognizes GRS as a national partner for the development and implementation of an effective, high quality HIV and AIDS prevention strategy that includes a community based model, advocacy, partnership and resource development.
- 2.6 MoE recognizes GRS as an institution responsible for developing Zambia’s sport-for-development HIV and AIDS strategy.

ARTICLE 3

3.0 Competent Authorities.

The competent authorities for purposes of the implementation of this Agreement shall be:

- 3.1 The GRS Secretary as designated below.
- 3.2 This MoU also recognizes the close relationship that exists between GRS and its implementing partners.
- 3.3 The Government of the Republic of Zambia recognizes that GRS needs to enter into partnerships with local organisations in order to effectively implement GRS’s HIV and AIDS strategy.
- 3.4 The Government of the Republic of Zambia designated its MoE to be legally represented in this matter by the Permanent Secretary Human Resource and Administration (HRA) of MoE

ARTICLE 4

4.0 Obligations of both Parties

Obligations of the Ministry of Education

Under this agreement and subject to the Project Activity MoUs that may be entered into hereafter, GRS may furnish assistance to the people of Zambia for the purpose of education and development in accordance with the priorities of the MoE.

- 4.1 GRS shall identify, in consultation with the relevant Government Ministry departments and other MoE recognized organisations, specific geographical areas of Zambia and projects requiring external assistance.
- 4.2 The term “**Project Activities**” shall mean all activities carried out by GRS for the benefit of the youth of Zambia
- 4.3 The term “**Project Materials**” shall mean all approved commodities, equipment, vehicles, materials and other property that are used by GRS in support of its Project Activities, or for the distribution to the people of Zambia or to the refugees within the scope of the Project Activities.
- 4.4 GRS may participate in implementing donor-funded projects, through various MoE departments as a sole consultant or in joint venture with other Government recognised Non-Governmental Organisations.
- 4.5 The MoE shall grant to GRS and its staff authorization to maintain and operate an external banking account for funds originating from external sources and the balance of such account shall be transferable into any freely convertible foreign currency.
- 4.6 The MoE will grant GRS the right to visit any area of the country not otherwise prohibited by law, and to discuss Project Activities with current and potential Implementing Partners and others involved in the project.
- 4.7 The MoE shall co-operate with GRS in obtaining monitoring and evaluation reports on Project Activities to be used in informing GRS donors on the effectiveness of its contribution and in raising additional support.
- 4.8 The MoE shall allow GRS to enter into public/ or private donor agreements that support programmed requirements.
- 4.9 The MoE will enable GRS to participate in Ministry-organised trainings, workshops, seminars and conferences that are deemed relevant to the advancement of GRS Project Activities and to the health and education of the young people of Zambia.

Obligations of GRS

- 4.10 GRS will provide leadership in establishing standards of good practice, and in applying high quality, sustainable, evidence-based HIV and AIDS programmes.
- 4.11 GRS will recognize and co-operate with other key bodies of the Government of the Republic of Zambia including the Ministry of Sport and Child Development, Ministry of Community Development and Social Services, and the Ministry of Health.
- 4.12 GRS will assist in attaining the objectives of the NASF 2006 2010. In particular, GRS will:
 - (i) Work with the Government of the Republic of Zambia to intensify its prevention programmers by implementing the GRS evidence-based and

comprehensive curriculum. The GRS curriculum encourages abstinence among unmarried youth, faithfulness among the married, and condom use for discordant couples, HIV+ individuals, and for individuals who are at risk and/or unable to abstain or to remain faithful to an uninfected partner. Additionally, GRS aims to break down stigma and discrimination against people living with HIV and AIDS (PLHA), open dialogue between Zambian youth and Peer Educators on HIV risk factors, and to teach young people life skills live HIV and AIDS free.

- (ii) Promote a comprehensive set of communication objectives aimed at improving knowledge, behaviour change towards safer sexual practices, accessing VCT and referrals to treatment, care and support services, as well as to mitigate stigma and discrimination.
 - (iii) Strengthen the MoE's capacity by identifying potential peer educators to be trained through ToCs in the GRS curriculum.
 - (iv) Collaborate with the Government of the Republic of Zambia in matters pertaining to the indicative core strategies of NASF 2006-2010 and in matters pertaining to the prevention of HIV and AIDS in Zambia.
- 4.13 GRS will seek to assist the educational community in Zambia to improve its outreach to Zambian youth in the field of HIV and AIDS, thereby promoting community benefits.
- 4.14 GRS shall maintain a Country Office in Zambia for the purposes of monitoring, coordinating and promoting all aspects of its work in Zambia. GRS will be responsible for the transportation and housing of all non-Zambian staff from the time of their arrival in Zambia.
- 4.15 GRS shall provide monitoring, evaluation, oversight and accountability on project activities and use of resources.
- 4.16 GRS shall recruit and pay wages of all local staff working under its employment and in accordance with the labour statutes and regulations of Zambia. GRS shall also remunerate all local staff according to the organisation's ability to pay.
- 4.17 GRS shall, where possible, raise funds and manage those funds received from donors for specific projects in Zambia.
- 4.18 In its role as MoE's partner, GRS will act in the national interests and take into account the priorities of Zambia's educational needs. GRS shall endeavor to have programming activities complement the MoE Vision and Development Plans.

ARTICLE 5

